### **Follow-up of Adverse Events**

Every reasonable effort will be made to follow up with subjects who have AEs. Any subject who has an ongoing AE that is possibly related or related to the IMP or study procedures at the Follow-up visit will be followed up, where possible, until resolution or until the unresolved AE is judged by the Investigator (or designee) to have stabilized. This will be completed at the Investigator's (or designee's) discretion. Any subject who has an ongoing AE that is not related or unlikely related to the IMP or study procedures at the Follow-up visit can be closed out as ongoing at the Investigator's discretion.

### **Adverse Drug Reactions**

All noxious and unintended responses to an IMP (i.e., where a causal relationship between an IMP and an AE is at least a reasonable possibility) related to any dose should be considered as adverse drug reactions.

For marketed medicinal products, a response to a drug which is noxious and unintended, and which occurs at doses normally used in man for prophylaxis, diagnosis, or therapy of diseases or for modification of physiological function is to be considered an adverse drug reaction.

An unexpected adverse drug reaction is defined as an adverse reaction, the nature or severity of which is not consistent with the applicable product information (e.g., Investigator's Brochure for an unapproved IMP).

### **Serious Adverse Events**

A serious AE (SAE) is defined as any untoward medical occurrence that at any dose either:

- results in death
- is life-threatening
- requires inpatient hospitalization or prolongation of existing hospitalization
- results in persistent or significant disability/incapacity (disability is defined as a substantial disruption of a person's ability to conduct normal life functions)
- results in a congenital anomaly/birth defect
- results in an important medical event (see below).

Important medical events that may not result in death, be life-threatening, or require hospitalization may be considered SAEs when, based upon appropriate medical judgment, they may jeopardize the subject and may require medical or surgical intervention to prevent one of the outcomes listed in this definition.

Instances of death or congenital abnormality, if brought to the attention of the Investigator at any time after cessation of the study treatment and considered by the Investigator to be possibly related to the study treatment, will be reported to the Protocol Safety Review Team (PSRT).

#### Definition of Life-threatening

An AE is life-threatening if the subject was at immediate risk of death from the event as it occurred (i.e., does not include a reaction that might have caused death if it had occurred in a more serious form). For instance, drug-induced hepatitis that resolved without evidence of hepatic failure would not be considered life-threatening even though drug-induced hepatitis can be fatal.

#### Definition of Hospitalization

Adverse events requiring hospitalization should be considered serious. In general, hospitalization signifies that the subject has been detained (usually involving an overnight stay) at the hospital or emergency ward for observation and/or treatment that would not have been appropriate at the Clinical Research Unit (CRU). When in doubt as to whether hospitalization occurred or was necessary, the AE should be considered as serious.

Hospitalization for elective surgery or routine clinical procedures, which are not the result of an AE, need not be considered AEs and should be recorded on a Clinical Assessment Form and added to the electronic Case Report Form. If anything untoward is reported during the procedure, this must be reported as an AE and either 'serious' or 'nonserious' attributed according to the usual criteria.

### **Serious Adverse Event Reporting**

Food and Drug Administration reportable AEs are AEs that are associated with the use of the drug and are serious and unexpected. Food and Drug Administration-reportable AEs will be reported by the study site to the PSRT and the responsible Institutional Review Board (IRB).

The PSRT will be notified in writing (e.g., facsimile) within 24 hours of when an AE that is potentially FDA-reportable is first recognized or reported.

Subsequently, a written confirmation or summary of the AE (using FDA Form 3500A or equivalent) will be sent to the Sponsor within 3 working days of the original notification.

The IRB will be notified of any FDA-reportable AEs within the timeframe required by the IRB. The IRB Serious and Unexpected Adverse Experience Submission Form will be completed and submitted with the copy of the written confirmation or summary of the AE.

The responsibility for reporting SAEs will be transferred to the Sponsor 30 days after the end of the study.

**Pregnancy**

Pregnancy (maternal or paternal exposure to study drug) does not meet the definition of an AE. However, to fulfill regulatory requirements any pregnancy should be reported following the serious AE process to collect data on the outcome for both mother and fetus.

**Appendix 2: Clinical Laboratory Evaluations**

Clinical chemistry:	Hematology:	Urinalysis:
Alanine aminotransferase Albumin a Alkaline phosphatase Aspartate aminotransferase Blood urea nitrogen Calcium Chloride Creatinine Gamma-glutamyl transferase Glucose (random) Potassium Sodium Total bilirubin b Total protein a Uric acid Fibrinogen C-reactive protein	Hematocrit Hemoglobin Mean cell hemoglobin Mean cell hemoglobin concentration Mean cell volume Platelet count Red blood cell (RBC) count RBC distribution width White blood cell (WBC) count WBC differential: Basophils Eosinophils Lymphocytes Monocytes Neutrophils  Coagulation profile: Activated partial thromboplastin time International normalized ratio Prothrombin time	Bilirubin Blood Color and appearance Glucose Ketones Leukocyte esterase Nitrite pH Protein Specific gravity Urobilinogen Microscopic examination (if protein, leukocyte esterase, nitrite, or blood is positive)
Cytokine panel IL-1 $\beta$ IL-6 TNF- $\alpha$		
Lipid panel (fasted)c Cholesterol Low density lipoprotein High density lipoprotein Triglycerides		
Serology d :	Drug screen e :	Hormone panel - females only:
Anti-hepatitis B surface antibody Anti-hepatitis B core antibody Hepatitis B surface antigen Hepatitis C antibody Human immunodeficiency (HIV-1 and HIV-2) Combo Ag/Ab HIV-1/HIV-2 immunoassay	Including but not limited to: Amphetamines/methamphetamines Barbiturates Benzodiazepines Cocaine (metabolite) Methadone Phencyclidine Opiates Tetrahydrocannabinol/Cannabinoids cotinine Alcohol f Alcohol breath test f	Follicle-stimulating hormone d (postmenopausal females only) Serum pregnancy test (human chorionic gonadotropin) g

a Calculated globulin and albumin:globulin ratio will be derived.

b Direct and indirect bilirubin will be analyzed if total bilirubin is elevated.

c Fasted lipid panel only included as indicated in the Schedule of Assessments ([Appendix 6](#)).

d Only analyzed at Screening.

e Urine test to include cotinine.

f Alcohol breath test (not included at Screening).

g Performed at Screening, Day -1, and Follow-up for all females.

### Appendix 3: Total Blood Volume

The following blood volumes will be withdrawn for each subject.

	Volume per blood sample (mL)	Maximum number of blood samples	Total amount of blood (mL)
Clinical laboratory evaluations	12.5	8	100
Serology	3.5	1	3.5
Coagulation	2.7	8	21.6
CPT31 pharmacokinetics	2	18	36
Immunogenicity	2	4	8
Total:			169.1

If extra blood samples are required, the maximum blood volume to be withdrawn per subject will not exceed 400 mL.

## Appendix 4: Contraception Guidance

### Definitions

**Women of Childbearing Potential:** premenopausal females who are anatomically and physiologically capable of becoming pregnant following menarche.

**Women of Nonchildbearing Potential:**

1. **Surgically sterile:** females who are permanently sterile via hysterectomy, bilateral salpingectomy, and/or bilateral oophorectomy by reported medical history and/or medical records. Surgical sterilization to have occurred a minimum of 6 weeks, or at the Investigator's discretion, prior to Screening.
2. **Postmenopausal:** Females at least 45 years of age with amenorrhea for 12 months without an alternative medical reason with confirmatory follicle-stimulating hormone (FSH) levels of  $\geq 40$  mIU/mL. The amenorrhea should not be induced by a medical condition such as anorexia nervosa, hypothyroid disease or polycystic ovarian disease, or by extreme exercise. It should not be due to concomitant medications that may have induced the amenorrhea such as oral contraceptives, hormones, gonadotropin-releasing hormones, anti-estrogens, or selective estrogen receptor modulators. Women aged  $> 60$  years old whose FSH values are not  $\geq 40$  mIU/L may be included at the discretion of the Investigator and in consultation with the Sponsor.

**Fertile male:** a male that is considered fertile after puberty.

**Infertile male:** permanently sterile male via bilateral orchiectomy.

### Contraception Guidance

#### Female Subjects

Female subjects who are of nonchildbearing potential will not be required to use contraception. Female subjects of childbearing potential must be willing to use 2 methods (1 primary and 1 secondary method) of birth control from the time of signing the Informed Consent Form (ICF) until 90 days after the Follow-up visit. Primary (non-barrier) methods of contraception include:

- hormonal injection (as prescribed)
- combined oral contraceptive pill or progestin/progestogen-only pill (as prescribed)
- combined hormonal patch (as prescribed)
- combined hormonal vaginal ring (as prescribed)
- hormonal IUD
- surgical method performed at least 3 months prior to the Screening Visit:
  - bilateral tubal ligation

- Essure® (hysteroscopic bilateral tubal occlusion) with confirmation of occlusion of the fallopian tubes
- hormonal implant
- vasectomized male partner (sterilization performed at least 90 days prior to the Screening Visit, with verbal confirmation of surgical success, and the sole partner for the female subject)

Secondary (barrier) methods of contraception include:

- male condom with spermicide
- female condom with spermicide
- over-the-counter sponge with spermicide
- cervical cap with spermicide (as prescribed)
- hormonal or non-hormonal intrauterine device (IUD)
- diaphragm with spermicide (as prescribed).

Female subjects of childbearing potential should refrain from donation of ova from Check-in (Day -1) until 90 days after the Follow-up visit.

### **Male Subjects**

Male subjects will be surgically sterile for at least 90 days, with documented azoospermia, or when sexually active with female partners of childbearing potential will be required to use a male condom with spermicide (even if subject has a history of vasectomy) from Check-in until 90 days after the Follow-up visit. Sexual intercourse with female partners who are pregnant or breastfeeding should be avoided unless condoms are used from the time of the first dose until 90 days after the Follow-up visit. Male subjects are required to refrain from donation of sperm from Check-in until 90 days after the Follow-up visit.

### **Sexual Abstinence and Same-sex Relationships**

For subjects who practice true abstinence, subjects must be abstinent for at least 6 months prior to Screening and must agree to remain abstinent from the time of signing the ICF until 90 days after the Follow-up visit.

A subject in a same-sex relationship at the time of signing the ICF must agree to refrain from engaging in a heterosexual relationship from the time of signing the ICF until 90 days after the Follow-up visit.

## **Appendix 5: Regulatory, Ethical, and Study Oversight Considerations**

### **Regulatory and Ethical Considerations**

This study will be conducted in accordance with the protocol and with the following:

- Consensus ethical principles derived from international guidelines including the Declaration of Helsinki and Council for International Organizations of Medical Sciences International Ethical Guidelines.
- Applicable International Conference on Harmonisation (ICH) Good Clinical Practice (GCP) Guidelines.
- Applicable laws and regulations.

The protocol, protocol amendments, Informed Consent Form (ICF), Investigator Brochure, and other relevant documents (e.g., advertisements) must be submitted to an Institutional Review Board (IRB) by the Investigator and reviewed and approved by the IRB before the study is initiated.

Any amendments to the protocol will require IRB and regulatory authority (as locally required) approval before implementation of changes made to the study design, except for changes necessary to eliminate an immediate hazard to study subjects. All protocol amendments must be approved by the NIAID Division of AIDS at the National Institutes of Health.

The Investigator will be responsible for the following:

- Providing written summaries of the status of the study to the IRB annually or more frequently in accordance with the requirements, policies, and procedures established by the IRB.
- Notifying the IRB of SAEs or other significant safety findings as required by IRB procedures.
- Providing oversight of the conduct of the study at the site and adherence to requirements of 21 Code of Federal Regulations (CFR), ICH guidelines, the IRB, European Regulation 536/2014 for clinical studies (if applicable), and all other applicable local regulations.

### **Finances and Insurance**

Financing and insurance will be addressed in a separate agreement.

### **Informed Consent**

Prior to starting participation in the study, each subject will be provided with a study-specific ICF giving details of the study drugs, procedures, and potential risks of the study. Subjects will be instructed that they are free to obtain further information from the Investigator (or designee) and that their participation is voluntary and they are free to withdraw from the

study at any time. Subjects will be given an opportunity to ask questions about the study prior to providing consent for participation.

Following discussion of the study with Clinical Research Unit (CRU) personnel, subjects will sign 2 copies of the ICF in the presence of a suitably trained member of staff to indicate that they are freely giving their informed consent. One copy will be given to the subject, and the other will be maintained in the subject's records.

Subjects must be re-consented to the most current version of the ICF(s) during their participation in the study.

### **Subject Data Protection**

Subjects will be assigned a unique identifier and will not be identified by name in electronic Case Report Forms (eCRFs), study-related forms, study reports, or any related publications. Subject and Investigator personal data will be treated in compliance with all applicable laws and regulations. In the event the study protocol, study report, or study data are included in a public registry, all identifiable information from individual subjects or Investigators will be redacted according to applicable laws and regulations.

The subject must be informed that his/her personal study-related data will be used by the Sponsor in accordance with local data protection law. The level of disclosure must also be explained to the subject. The subject must also be informed that his/her study-related data may be examined by Sponsor or Contract Research Organization (CRO) auditors or other authorized personnel appointed by the Sponsor, by appropriate IRB members, and by inspectors from regulatory authorities such as the Food and Drug Administration (FDA).

### **Disclosure**

All information provided regarding the study, as well as all information collected and/or documented during the course of the study, will be regarded as confidential. The Investigator (or designee) agrees not to disclose such information in any way without prior written permission from the Sponsor.

### **Data Quality Assurance**

The following data quality steps will be implemented:

- All relevant subject data relating to the study will be recorded on eCRFs unless directly transmitted to the Sponsor or designee electronically (e.g., laboratory data). The Investigator is responsible for verifying that data entries are accurate and correct by electronically signing the eCRF.
- The Investigator must maintain accurate documentation (source data) that supports the information entered in the eCRF.
- The Investigator must permit study-related monitoring, audits, IRB review, and regulatory agency inspections and provide direct access to source data documents.

- The Sponsor or designee is responsible for the data management of this study including quality checking of the data. Predefined agreed risks, monitoring thresholds, quality tolerance thresholds, controls, and mitigation plans will be documented in a risk management register. Additional details of quality checking to be performed on the data may be included in a Data Management Plan.
- A Study Monitor will perform ongoing source data verification to confirm that data entered into the eCRF by authorized site personnel are accurate, complete, and verifiable from source documents; that the safety and rights of subjects are being protected; and that the study is being conducted in accordance with the currently approved protocol and any other study agreements, ICH GCP, and all applicable regulatory requirements.
- Records and documents, including signed ICFs, pertaining to the conduct of this study must be retained by the Investigator in accordance with 21 CFR 312.62(c) unless local regulations or institutional policies require a longer retention period. No records may be destroyed during the retention period without the written approval of the Sponsor. No records may be transferred to another location or party without written notification to the Sponsor.

### **Investigator Documentation Responsibilities**

All individual, subject-specific study data will also be entered into a 21 CFR Part 11-compliant electronic data capture (EDC) system on an eCRF in a timely fashion.

All data generated from external sources (e.g., laboratory and bioanalytical data), and transmitted to the Sponsor or designee electronically, will be integrated with the subject's eCRF data in accordance with the Data Management Plan.

An eCRF must be completed for each enrolled subject who undergoes any Screening procedures, according to the eCRF completion instructions. The Sponsor, or CRO, will review the supporting source documentation against the data entered into the eCRFs to verify the accuracy of the electronic data. The Investigator will ensure that corrections are made to the eCRFs and that data queries are resolved in a timely fashion by the study staff.

The Investigator will sign and date the eCRF via the EDC system's electronic signature procedure. These signatures will indicate that the Investigator reviewed and approved the data on the eCRF, data queries, and site notifications.

### **Publications**

If on completion of the study the data warrant publication, the Investigator may publish the results in recognized (refereed) scientific journals subject to the provisions of the clinical study agreement (CSA). Unless otherwise specified in the CSA, the following process will occur:

If the Investigator expects to participate in the publication of data generated from this site, the institution and Investigator will submit reports, abstracts, manuscripts, and/or other presentation materials to the Sponsor for review before submission for publication or

presentation. The Sponsor will have 60 days to respond with any requested revisions including, without limitation, the deletion of confidential information. The Investigator will act in good faith upon requested revisions, except the Investigator will delete any confidential information from such proposed publications. The Investigator will delay submission of such publication or presentation materials for up to an additional 90 days in order to have a patent application(s) filed.

**Appendix 6: Schedule of Assessments**

**Schedule of Assessments**

Study Procedures	Screening Day -28 to Day -2	Day -1	Treatment Period		Follow-up (28-30 days postdose)
			Days 1 to 6		
Informed consent	X				
Inclusion/exclusion criteria	X	X			
Demographic data	X				
Medical and surgical history	X	X a			
Urinary drug screen	X	X			
Alcohol breath test		X			
HIV, hepatitis B, and hepatitis C tests	X				
Serum pregnancy test b	X	X			X
Height and body weight	X c	X			
Study residency:					
Check-in		X			
Check-out			Day 6		
Nonresidential visit	X				X
Study drug administration:					
CPT31 or placebo			Day 1 (0 h)		
Pharmacokinetics:					
Blood sampling d			Day 1 predose, 0.5 h ( $\pm$ 3 min), 1 h ( $\pm$ 6 min), 2 h ( $\pm$ 12 min), 4 h ( $\pm$ 30 min), 6 h ( $\pm$ 30 min), 8 h ( $\pm$ 30 min), 10 h ( $\pm$ 30 min), 12 h ( $\pm$ 30 min), 16 h ( $\pm$ 30 min), Day 2 (24 h, $\pm$ 30 min), Day 3 (48 h, $\pm$ 4 h), Day 4 (72 h, $\pm$ 4 h), Day 5 (96 h, $\pm$ 4 h), and Day 6 (120 h, $\pm$ 4 h)		
Urine sampling d, i			Day 1 predose (spot collection) and 0 to 4 h ( $\pm$ 15 min), 4 to 8 h ( $\pm$ 15 min), Day 1 to Day 2 (8 to 24 h, $\pm$ 15 min), Day 2 to Day 3 (24 to 48 h, $\pm$ 15 min), and Day 3 to Day 4 (48 h to 72 h $\pm$ 15 min)		

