### 1.5. Summary of Nonclinical Pharmacokinetics

Following intravenous (IV) or SC administration (1 mg/kg) in Sprague-Dawley rats, the apparent plasma terminal elimination half-life (t1/2) of CPT31 was 3.2 and 5.5 hours, respectively, and SC bioavailability was 53%. Similarly, following IV or SC administration (1 or 3 mg/kg, respectively) in cynomolgus macaques, the t1/2 of CPT31 was 7 and 18.6 hours, respectively, and SC bioavailability was 78%. CPT31 given IV to Sprague-Dawley rats or monkeys has a low volume of distribution (134 mL/kg and 96 mL/kg, respectively), suggesting that it is largely confined to the plasma compartment. Plasma protein binding studies revealed that 5  $\mu$ M CPT31 is  $\geq$ 96% bound in rat, minipig, dog, monkey, and human plasma.

Both Cmax and AUC of CPT31 upon SC administration to Sprague-Dawley rats are linear (but not fully dose proportional) at increasing dose levels up to 40 mg/kg. Terminal half-life is consistently between 4 and 8 hours at dose levels ranging from 3-75 mg/kg.

A distribution/excretion study using radioactive [I]-CPT31 suggested that CPT31 is eliminated via renal clearance, as expected for a mid-molecular weight compound (average 9,029 Daltons). Composed of D-peptides, CPT31 is not expected to enter peptide catabolic pathways.

Non-parametric superposition of available cynomolgus macaques PK data (Table 1) and allometric scaling to humans predicts that a 0.03 mg/kg SC injection every third day would give a trough level  $\sim$ 13-22 nM (117-199 ng/mL). Therefore, this dose is tentatively set as the expected human therapeutic dose in order to achieve a trough CPT31 level of  $\geq$ 4  $\times$  the

serum-adjusted IC90 against diverse strains in human PBMCs (~16 nM), as described above. However, the PK profile in humans remains to be established, and the estimated effective dosing will change accordingly.

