### **3.1. Overall Study Design and Plan**

This study will comprise a placebo-controlled, double-blind, single-dose, sequential-group design. Overall, it is planned for 32 healthy subjects to be studied in 4 groups (Groups A1 to A4), with each group consisting of 8 subjects. In each group, 6 subjects will be randomized to receive SC CPT31 and 2 subjects will be randomized to receive matching placebo.

Potential subjects will be screened to assess their eligibility to enter the study within 28 days prior to the first dose administration.

Each subject will participate in 1 treatment period only. Subjects will reside at the Clinical Research Unit (CRU) from Day -1 (the day before dosing) to Day 6. All subjects will return for a Follow-up visit 28 to 30 days after dosing.

Based on the ongoing review of the safety, tolerability, and PK results, additional nonresidential visits may be required. The number of additional visits per subject will not exceed 3 and will not extend beyond 30 days after dose administration.

[figure not shown]
All groups will be divided into 2 cohorts, with each cohort being dosed 72 hours apart. The first (sentinel) cohort will comprise 2 subjects, with 1 subject receiving CPT31 and 1 subject receiving placebo. The second cohort will comprise 6 subjects, with 5 subjects receiving CPT31 and 1 subject receiving placebo.

The maximum total duration of study participation for each subject (from Screening through Follow-up visit) is anticipated to be approximately 8 weeks.

Dose escalation will occur a minimum of 7 days after all subjects complete all Day 6 assessments in the previous dose group.

[figure not shown]
An overview of the study design is shown in [Figure 1](#) and the planned dose levels in are shown in [Figure 2](#). A Schedule of Assessments is presented in [Appendix 6](#).

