### 3.5. Selection of Doses in the Study

Based on activity in human PBMCs infected with diverse primary isolates, the estimated effective serum trough concentration of CPT31 is 16 nM (145 ng/mL) (4x the serum-adjusted IC90 in PBMCs).

Human PK modeling predicts that a dose of 0.03 mg/kg administered every third day will be optimal to maintain CPT31 serum trough levels in a narrow range (~13-22 nM, 117-199 ng/mL) that is close to the target trough concentration of 16 nM while minimizing total exposure (Cmax ~50 nM, 452 ng/mL) over the course of an envisioned future short-duration (~2-week) multiple ascending dose human study. We propose a starting dose of 0.01 mg/kg in this first-in-human single ascending dose study, with subsequent dose escalations to 0.04 mg/kg (4-fold increase), 0.12 mg/kg (3-fold increase), and 0.24 mg/kg (2-fold increase). The safety margins for the 0.01 mg/kg human dose relative to rat and monkey NOAELs are 97 and 320, respectively (Table 2).

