8.1.1. Calculation of the Summary Statistics

For continuous data the following rules will be applied:

- Missing values will not be imputed, unless specifically stated otherwise.
- Unrounded data will be used in the calculation of summary statistics.
- If the number of subjects with valid observations (n) < 3 , summary statistics will not be calculated, with the exception of n , minimum, and maximum.
- As Early Termination data is not associated with any scheduled timepoint, it will be excluded from all calculations of summary statistics.

For categorical data the following rules will be applied:

- If the categories of a parameter are ordered (eg, AE severity), all categories between the possible minimum and maximum categories will be included, even if $n = 0$ for a given category. If the categories are not ordered (eg, race), only those categories for which there is at least 1 subject represented will be included.
- Missing values will not be imputed, with the exception of AEs where the 'worst-case' approach will be taken (see [Section 8.6.1](#)), or unless specifically stated otherwise. A 'missing' category will be included for any parameter for which information is missing. This will ensure that the population size totals are consistent across different parameters.

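### Cumulative urinary recovery (Fe) is a 0–72 h value that understates the total, with no extrapolation planned, and the SAP's unit for CLR is the reciprocal of its own formula

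*Protocol*

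**What the plan says.** **Urine.** Protocol Appendix 6 lists a predose spot sample, then collections over 0–4, 4–8, 8–24 and 24–48 h, "and Day 3 to Day 4 (48 h to 72 h". Protocol Section 7.1.1 and a footnote to the schedule restrict urine PK to male subjects.

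**Plasma and residence.** The same schedule samples plasma to 120 h on Day 6. Protocol Section 3.1: "Subjects will reside at the Clinical Research Unit (CRU) from Day -1 (the day before dosing) to Day 6".

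**Endpoints.** Ae, Fe and CLR are secondary endpoints in Protocol Section 2.2.2 and SAP Section 3.2, with no time limit attached.

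**Derivation.** SAP Section 8.5.1 obtains cumulative Ae and Fe by summing the intervals to the end of collection. It defines CLR as Ae(0–t2)/AUC(0–t2) over the same interval. Its parameter table gives CLR in `h*xg/mL/mg` and CL/F in L/h.

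**Summaries.** SAP Section 8.5.3 tabulates excretion parameters by treatment and time interval, with no table pooled over doses. Under SAP Section 8.1.1, when fewer than three subjects have valid data, "summary statistics will not be calculated, with the exception of" n, minimum and maximum.

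**What is known of the half-life.** No human value is given. In cynomolgus macaques, the IV and SC half-life "of CPT31 was 7 and 18.6 hours, respectively, and SC bioavailability was 78" percent (Protocol Section 1.5). Protocol Section 3.5 says that 0.03 mg/kg "administered every third day will be optimal to maintain CPT31 serum trough levels in a narrow range (~13-22 nM, 117-199 ng/mL"), with a peak of about "50 nM, 452 ng/mL) over the course of an envisioned future short-duration (~2-week) multiple ascending dose human study".

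**The concern.** CPT31 is expected to leave the body through the kidney (Protocol Section 1.5), and renal tubular degeneration was a leading toxicity finding in rats and monkeys (Sections 1.4.1 and 1.4.2). The renal parameters therefore matter more here than in most first-in-human studies.

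Fe as planned stops at 72 h, although plasma is followed for another 48 h in subjects who are still in the unit. The SAP reports the extrapolated share of plasma AUC and has a 30% level at which AUC0–inf may be excluded, but it has no counterpart for incomplete urine recovery. If a 0–72 h Fe appears in a report simply as Fe, it will be taken as total recovery and will be too low by an unknown amount.

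CLR would let the reader repair this, but as labelled it cannot be set against CL/F. Males-only sampling also thins the by-dose tables, and the SAP, written against Protocol Version 4.0 (the version that introduced the restriction), does not allow for it.

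**Working it through.** **1. Reproduce the protocol's figures.** With a molecular weight of "average 9,029 Daltons", nM = 1000 × (ng/mL)/9,029. Then 117 gives 12.96, 199 gives 22.04 and 452 gives 50.06 nM. The stated 13, 22 and 50 nM agree.

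**2. Half-lives implied by the repeat-dose predictions** (inferred; every-third-day dosing, so the trough is at 72 h).
- Trough rising by accumulation from 13 to 22 nM: exp(−72k) = 1 − 13/22 = 0.409, so t1/2 = 72 × ln 2 / −ln 0.409 = 55.8 h.
- Peak to trough, t1/2 = (72 − Tmax) × ln 2 / ln(Cmax/Ctrough), with Tmax assumed at 4–12 h: 50/22 gives 51–57 h and 50/13 gives 31–35 h.

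I carry forward 33 h (middle of 31–35), 56 h, and the unscaled monkey SC value of 18.6 h.

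**3. Share of eventual excretion missed.** If CLR is constant, the share of excretion after time T equals the share of AUC after T. With first-order absorption and k = ln 2/t1/2,

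S(T) = [ka·exp(−kT) − k·exp(−ka·T)]/(ka − k), with ka chosen so that ln(ka/k)/(ka − k) = Tmax.

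Example: t1/2 56 h and Tmax 4 h give k = 0.01238 and ka = 1.144 per hour. S(72) = 1.144 × 0.4102/1.1316 = 0.415 (the second term is negligible).

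| t1/2 | missed after 72 h | missed after 120 h |
|---|---|---|
| 18.6 h | 7.2–9.0% | 1.2–1.5% |
| 33 h | 22.5–24.4% | 8.2–8.9% |
| 56 h | 41.5–43.0% | 22.9–23.7% |

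Each range spans Tmax 4–12 h. As a sensitivity check, fix the 72 h concentration at 26% (13/50) or 44% (22/50) of peak and take absorption half-lives of 2–8 h. This gives 15–39% missed after 72 h and 3–20% after 120 h. At 18.6 h, the same absorption range gives 8–12% and 1–2%.

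**4. Unit of CLR.** Ae/AUC has unit mg/(h·xg/mL), a volume per time. The SAP lists h·xg/mL/mg, which is AUC/Ae. If x is micro, 1 mg/(h·µg/mL) = 1 L/h. If x is nano, 1 mg/(h·ng/mL) = 1,000 L/h.

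**5. Total Fe from planned quantities.** Ae(0–inf) = CLR × AUC0–inf and dose = (CL/F) × AUC0–inf, so Fe(0–inf) = 100 × CLR/(CL/F). This is a percentage of the SC dose and so includes bioavailability. Illustration: a drug cleared only by the kidney, with the monkey bioavailability of 78%, has Fe(0–inf) = 78%. Its Fe(0–72 h) would be 78 × 0.570 to 78 × 0.585 = 44–46% at t1/2 56 h, and 78 × 0.910 to 78 × 0.928 = 71–72% at 18.6 h.

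**6. Males per group.** Enrolment by sex is not specified. Among 6 active subjects:
- 50% male: P(fewer than 3) = (1 + 6 + 15)/64 = 34%; all four groups reach 3 with probability 0.656^4, about 19%.
- 70% male: P = 0.0007 + 0.0102 + 0.0595 = 7%; all four reach 3 with probability 0.930^4 = 75%.

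Pooled over doses, the expected number of CPT31 males is 4 × 6 × 0.5 = 12, or 16.8 at 70%.

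**The case against.** The strongest reply is that the loss may be small and is already visible. No human half-life is stated, Protocol Section 1.5 says human PK is still to be established, and at the monkey value only 7–9% is missed. The SAP tabulates Ae and Fe by interval, computes CLR over a matched interval and allows additional parameters. Most of this stands, and it is why the shortfall is given as a range. It does not remove the point: the endpoint carries no interval label, and no estimate of total recovery is committed to.

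Four stronger readings are tempting but not supported.
- A reader might infer that the protocol predicts 26–44% of peak still circulating at 72 h in this study. Those are ratios formed from predictions for repeated dosing in a future study; no single-dose prediction is given. The 13/50 ratio may also pair a first-dose trough with an accumulated peak. Nor is a share of peak concentration the share of excretion missed.
- A low Fe might be read as non-renal clearance manufactured by the design. Fe is a percentage of an SC dose, and bioavailability was 53% in rats and 78% in monkeys. A value below 100% would not by itself show non-renal clearance, however long urine was collected.
- Small groups might be said to go unreported. The n, minimum and maximum remain, and every value is listed. The 34% also rests on an assumed 50% male share.
- Collection to 120 h might look necessary. At 56 h it still misses about 23%, at 18.6 h it gains little, and no urine quantification limit is given to show that late samples would be measurable.

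**Conclusion.** The concern holds in a limited form. Cumulative Ae and Fe are 0–72 h quantities that understate total urinary recovery in every scenario examined. The size depends on a human half-life that nobody yet knows: about 7–9% of eventual excretion at 18.6 h, and about 22–43% at the inferred 33–56 h. This assumes one compartment, constant CLR and Tmax of 4–12 h; slower absorption moves the figures as shown in the sensitivity check.

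CLR itself is sound, but its unit is wrong as written. That follows from comparing two places in SAP Section 8.5.1 and needs no model. The thin by-dose summaries are a possibility whose probability turns on the share of males enrolled. None of this affects the primary safety objective or the plasma parameters.

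**What to change.** In the SAP, before database lock:
1. Change the CLR unit to volume per time (L/h), so that it can be compared with CL/F.
2. Label cumulative Ae and Fe as 0–72 h, or with the actual interval if collection is incomplete. Add Fe(0–inf) = 100 × CLR/(CL/F) where AUC0–inf is reportable, with a note that it assumes constant CLR and is a percentage of the SC dose, bioavailability included. In the model, plasma to 120 h leaves 23–24% of AUC to extrapolate even at 56 h. That is under the 30% level in SAP Section 8.5.1.3, provided concentrations stay quantifiable to 120 h.
3. Beside the by-dose tables, add a summary of CLR and Fe pooled over all CPT31 males. Pooling presumes little dose dependence, so the by-dose values should stay in view.

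These items cost SAP and table-shell wording only and use data already planned.

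Optional: add 72–96 h and 96–120 h urine intervals. This needs a protocol amendment and two more 24 h collections and assays in males who are already resident. It would reduce the truncation but not remove it, and items 1–3 are needed either way.
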